4.6.1 INTRANASAL EXAMINATION

The intranasal examination can be completed without topical anesthesia using a nasal speculum. The speculum is gently inserted into the lower end of each of the nares. A light should be utilized to enhance visualization. The speculum is opened to expand the nares such that the nasal cavity can be carefully inspected.

The nasal cavity is inspected for gross ulceration, mass lesions, severe septal deviations or evidence of prior surgery/cautery. Any other gross abnormalities or irregularities should be documented accordingly.

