8 POTENTIAL RISKS AND BENEFITS TO HUMAN PARTICIPANTS

This is a non-significant risk (NSR) device study because of the use of marketed products and standard optometric assessments. This device has been granted marketing authorization by the US Food and Drug Administration (FDA) for the purpose of temporarily increasing tear production during stimulation.

Contact lenses in this study will be worn on a daily wear basis, with the participant continuing with their normal lenses and solutions, and with lenses being worn in accordance with their normal wear schedule. Adverse events and/ or complications in daily wear of soft contact lenses can occur (e.g.: inflammation and infection). When contact lenses are worn on a daily wear basis there is a small risk of an adverse event compared to not wearing contact lenses.

Anticipated risks from use of TrueTear may include: an increase in nasal secretions, uncomfortable sensations, epistaxis and other nasal irritations. The full list of potential adverse events from the use of the device is detailed in section 9 (Adverse Events) below.

Anticipated benefits may be a reduction in CL discomfort symptoms and longer comfortable wearing time of CLs over the course of the study.

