9.2.3 ANTICIPATED ADVERSE EVENTS

The following is a list of potential AEs associated with the use of TrueTear or TrueTear sham control:

- Nasal discomfort or pain
- Epistaxis
- Excessive sneezing
- Nasal irritation, paresthesia or numbness post-stimulation
- Nasal infection, abrasion or inflammation

[figure not shown]
- Skin irritation or hypersensitivity
- Headache (e.g., tension, migraine, etc.)
- Facial pain
- Excessive salivation
- Sensation of teeth vibrating
- Excessive rhinorrhea
- Temporary aggravation of nasal allergies
- Allergic reaction to contact materials

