The critical alpha level for statistical significance will be set at $p \leq 0.05$, with no adjustments for multiple comparisons. All participants who were evaluated will be used in the analysis. In the event of missing data, individual data points will be excluded in the analysis and not extrapolated from the collected data. As this is a proof of concept, additional statistical analysis may be conducted.

Dependent on the outcome of the study, analysis may be conducted on the contact lenses that have been collected. If the decision is made to not analyse the contact lenses then they will be destroyed according to University guidelines.

Additional analyses may be performed to examine the results observed relative to the device usage recorded by the device itself.

Safety assessments include adverse events, visual acuity and slit lamp biomicroscopy. Summaries by application will be prepared of the number and percentage of subjects reporting one or more adverse events, the number and percentage of subjects reporting one or more device-

related adverse events, the number and percentage of eyes with a clinically significant change in visual acuity at each follow-up exam and the number and percentage of eyes with a clinically significant change in slit lamp biomicroscopy at each visit. A clinically significant change in visual acuity is defined as a change of more than 2 lines (logMAR score change greater than 0.2). A clinically significant change in the slit lamp biomicroscopy parameters will be a change of 2 or more grades.

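### Section 12.1 plans no adverse-event summary by type, severity or seriousness and no summary of intranasal findings, so an arm difference in a specific nasal harm can be diluted in two pooled counts

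*Combined protocol and SAP*

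**What the plan says.** The safety paragraph of section 12.1 opens: "Safety assessments include adverse events, visual acuity and slit lamp biomicroscopy". It continues: "Summaries by application will be prepared of the number and percentage of subjects reporting one or more adverse events". The other three by-arm summaries are participants with a device-related AE, eyes with a clinically significant change in visual acuity, and eyes with a clinically significant slit-lamp change. Thresholds are defined for the two ocular measures. The same section adds: "As this is a proof of concept, additional statistical analysis may be conducted".

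Elsewhere the protocol puts the expected harm mainly in the nose:

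- Section 8: "Anticipated risks from use of TrueTear may include: an increase in nasal secretions, uncomfortable sensations, epistaxis and other nasal irritations".
- Section 9.2.3: "The following is a list of potential AEs associated with the use of TrueTear or TrueTear sham control". One of its 13 entries is "Nasal infection, abrasion or inflammation".
- Section 4.6.1 describes a speculum examination: "The nasal cavity is inspected for gross ulceration, mass lesions, severe septal deviations or evidence of prior surgery/cautery". Other gross abnormalities are also to be documented. No grading scale or threshold for change is given.

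On data capture, section 9.1 requires AEs found by examination to be recorded and treats any clinically relevant deterioration in a finding as an AE. Sections 9.2, 9.2.1 and 9.2.2 require seriousness, intensity and relationship to the device to be judged for each event.

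**The concern.** The planned safety tables follow the eye, while the exposure under test is daily intranasal use for about a month. The arms also differ in how far the probe goes in. Section 4.1.3 says the sham is modified to limit insertion depth, whereas section 5 has active users insert the tips fully. (Section 6 also tells sham users to insert the tips fully. That wording should be reconciled with section 4.1.3, but the depth limit is described as part of the sham hardware.) A nasal difference between arms is therefore plausible and is something a reader of the results would want to see.

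Of the attributes recorded for each AE, only relationship to the device reaches a planned table. Type, intensity and seriousness reach none. In the two counts each participant counts once, so a severe nasal event and a mild bout of sneezing weigh the same. The intranasal examination has no planned summary.

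**Working it through.** **1. Coverage.** The plan states no safety figure to reproduce, so the first check is a count.

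- Anticipated AEs in section 9.2.3: 13.
- Nasal: discomfort or pain; epistaxis; sneezing; irritation, paresthesia or numbness; infection, abrasion or inflammation; rhinorrhea; aggravated nasal allergies. That is 7 of 13 (54%), or 6 of 13 (46%) if sneezing is left out.
- Naming the eye: 0 of 13.
- Planned safety summaries in section 12.1: 4, of which 2 are ocular, 2 are all-AE counts and 0 are nasal.

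**2. Arm size.** Section 12.1 has about 80 randomized. Section 4.2.2 allows up to 120 randomized with a target of 80 completing. The allocation ratio is not stated. Assuming 1:1, the arms hold 40 or 60 participants. The documents give no AE rates, so every rate below is invented for illustration.

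**3. How far a difference can be hidden.** Suppose epistaxis occurs in 6 of 40 active users and 0 of 40 sham users (15% versus 0%). With six events in total, the two-sided Fisher p-value is 2 × C(40,6)/C(80,6) = 2 × 3,838,380/300,500,200 = 0.026. If 12 participants in each arm have some other AE, and the six with epistaxis are among those 12, the any-AE row reads 12 versus 12 (30% each). This is the extreme case.

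The device-related row would hide less. If all six events are judged at least possibly related, the active count is at least 6. The arms then look equal only if at least six sham participants have some other related event.

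**4. Expected dilution.** If nasal and other AEs are independent, the any-AE rate is 1 − (1 − nasal)(1 − background). A nasal difference therefore shrinks by the factor (1 − background).

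- 15% versus 0% with 30% background: 1 − 0.85 × 0.70 = 40.5% versus 30.0%. The 15-point difference becomes 10.5 points.
- 25% versus 2.5% with 30% background: 1 − 0.75 × 0.70 = 47.5% versus 1 − 0.975 × 0.70 = 31.75%. The 22.5-point difference becomes 15.75 points.

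For the second case, the table gives the power of a two-sided 0.05 comparison of two proportions. The plan specifies no safety test; power is used here only as a measure of visibility.

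| Row examined (40 per arm) | Difference, points | Power |
|---|---|---|
| Nasal AEs alone | 22.5 | 0.85 |
| Any AE, 10% background | 20.25 | 0.59 |
| Any AE, 30% background | 15.75 | 0.30 |
| Any AE, 50% background | 11.25 | 0.17 |

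With 60 per arm the pattern is the same: 0.96 for nasal AEs alone and 0.42 for any AE at 30% background.

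**The case against.** The strongest reply is that nothing is lost. Section 9.1 turns any clinically relevant nasal deterioration into a recorded AE, and section 9.2.2 sets a low bar for device-relatedness, since a possible link is enough. Serious events go to the sponsor within 24 hours and promptly to the ethics committee (section 9.3). The safety list is introduced by a word that does not make it exhaustive, extra analyses are allowed, and this is an exploratory study whose sample size was set empirically.

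Most of that stands, and it rules out several stronger readings that a reader might infer:

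- *Nasal injury would go uncounted.* Section 9.1 contradicts this. Only a finding judged not clinically relevant, or one never looked for, could escape.
- *No follow-up nasal examination is done.* The public text cannot show this. The visit schedule and the opening of section 4.5 are redacted.
- *A nasal difference would disappear altogether.* The device-related row limits the masking, and under independence the any-AE row shrinks the difference without removing it.
- *The trial could put no upper limit on nasal harm.* With no recorded nasal AE among 40 users, the one-sided 95% upper limit would be 1 − 0.05^(1/40) = 7.2%; with 60 it would be 4.9%. The recorded data would support that statement for clinically apparent events, although no planned table would display it.

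The reply does not answer the reporting gap. Permission to do more analysis commits no one to it, and tables chosen after the results are known carry less weight. The device-related count still pools event types.

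**Conclusion.** The point holds as a gap in the planned safety reporting. The visible section 12.1 specifies no AE table by type, severity or seriousness and no by-arm summary of intranasal findings, for a device whose anticipated harms are nasal in 7 of 13 entries and ocular in none. Followed as written, the tables would not separately display an arm difference in epistaxis or mucosal injury.

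The size of the dilution depends on the background AE rate, which the documents do not give. At an assumed 30% it removes 30% of a nasal difference from the any-AE row, and less from the device-related row. The worked figures rest on invented event rates, 1:1 allocation, 40 or 60 per arm and, in step 4, independence. The coverage finding needs none of these assumptions. The efficacy comparisons are unaffected. The change is worth making because it is cheap and the results may inform later studies.

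**What to change.** In section 12.1, keep the any-AE and device-related counts and add:

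1. A by-arm table of participants with each type of AE, showing the nasal and facial events of section 9.2.3 separately, with worst severity, seriousness and events leading to discontinuation.
2. The section 4.6.1 intranasal examination as a named safety assessment. For every post-screening visit at which the schedule already includes it, tabulate by arm the participants with a new or worse finding relative to screening. The investigators should state in advance what counts as a significant change, because section 4.6.1 has no scale, whereas section 12.1 defines one for both ocular measures.
3. The denominator for these tables, after reconciling the numbers randomized in sections 4.2.2 and 12.1.

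The cost is a small amount of extra table programming on data already recorded and one short definition. No new visit or procedure is required.

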9.2 ADVERSE EVENT EVALUATION

The Investigator should evaluate if each AE is serious, related to the applicable study device and anticipated using the following definitions.

A serious adverse event (SAE) is defined as any untoward medical occurrence that:

- It results in death (i.e., the AE actually causes or leads to death);
- It is life threatening (i.e., the AE places the participant at immediate risk of death);
- It requires or prolongs inpatient hospitalization. If a participant is hospitalized to undergo a medical or surgical procedure as a result of an AE, the event responsible for the procedure, not the procedure itself, should be recorded as the event. For example, if a participant is hospitalized to undergo coronary bypass surgery, the heart condition that necessitated the bypass should be recorded. Hospitalizations for diagnostic or elective surgical procedures or hospitalizations required to allow outcome measurement for the study should not be recorded as SAEs;
- It results in persistent or significant disability/incapacity (i.e., the AE results in substantial disruption of the participant's ability to conduct normal life functions);
- It results in a congenital anomaly/birth defect in a neonate/infant born to a mother exposed to the investigational device;
- It is considered a significant medical event by the Investigator based on medical judgment (e.g. may jeopardize the participant or may require medical/surgical intervention to prevent one of the outcomes listed above);
- It is considered sight-threatening by the Investigator.

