9.2.1 SEVERITY/INTENSITY

All AEs that occur during the course of the study must be reported on the Adverse Event CRF. The Investigator must determine the intensity of the event.

Mild	Awareness of sign or symptom, but easily tolerated
Moderate	Discomfort enough to cause interference with normal daily activities
Severe	Inability to perform normal daily activities

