9.2.2 RELATIONSHIP TO THE STUDY DEVICE

Definite	A clear cut causal relationship with the study device and no other possible cause
Probable	A causal relationship with the study device is likely although alternate etiologies are also possible
Possible	A causal relationship with study device is not definite, alternate etiologies are also possible
Not related	The AE has no causal relationship to study device and/or there is evidence of alternative etiology such as concurrent medication or illness.
Not applicable	The participant has not been exposed to the study device.

The AE will be determined to be device related, making it an adverse device effect (ADE), if it is identified to have had a definite, probable or possible causal relationship to the device.

An AE is unanticipated if the nature, severity, or frequency of the event is not consistent with either the known or foreseeable risk of AEs associated with the procedures involved in the research that are described in (a) the protocol-related documents, such as the EC-approved research protocol, user manuals and the current EC-approved informed consent document, and (b) other relevant sources of information such as product labeling and package inserts; or the expected natural progression of any underlying disease, disorder, or condition of the participant(s) experiencing the AE and the participant's predisposing risk factor profile for the AE.

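### Every adverse event is graded for intensity, but the planned adverse-event summaries by arm are yes/no counts that cannot show a shift towards stronger events.

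*Combined protocol and SAP*

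**What the plan says.** **Collected.** Section 9.2.1: "All AEs that occur during the course of the study must be reported on the Adverse Event CRF", and "The Investigator must determine the intensity of the event" on a mild, moderate or severe scale. Section 9.2: "The Investigator should evaluate if each AE is serious, related to the applicable study device and anticipated". Intensity is therefore mandatory, while seriousness, relatedness and anticipation carry the weaker "should". Section 9.2.2 classes an AE as device-related "if it is identified to have had a definite, probable or possible causal relationship to the device", which folds three grades of causality into one yes/no class with no intensity element.

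**Summarised by arm.** Section 12.1 names two AE summaries. The first is "Summaries by application will be prepared of the number and percentage of subjects reporting one or more adverse events". The second is "the number and percentage of subjects reporting one or more device"-related AE. The same paragraph adds two ocular summaries: eyes with a clinically significant visual acuity change, and "the number and percentage of eyes with a clinically significant change in slit lamp biomicroscopy at each visit".

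**Elsewhere.** Section 9.3 has serious AEs reported to the sponsor within 24 hours, and serious AEs and unanticipated problems notified to the ethics committee. Section 12.1 also permits further statistical analysis without naming any on AE intensity or seriousness.

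**The concern.** Both arms place a device in the nose, and section 9.2.3 gives a single list of anticipated events for the two devices, mostly nasal but also including facial pain and headache. Only the active device delivers current (section 4.1.3), and its users choose among five intensity levels (section 5). One plausible safety difference is therefore that events are stronger on the active device, and not only that more people have one.

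A per-participant yes/no count gives a mild event and a severe event the same weight. If intensity rises among people who would have reported an event in either arm, both planned AE rows stay the same. The trial would then report similar AE proportions without using the grades that could separate the arms. Section 4.1.2 describes relief of contact lens dryness as an investigational use, and section 12.1 says the results may inform later studies, so tolerability against sham is something a reader will want from this study.

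**Working it through.** The documents state no AE rate and no safety calculation, so there is no figure of theirs to reproduce. The check has two parts.

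**1. Attributes recorded against attributes tabulated by arm**

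| Attribute | Recorded | In a planned AE summary by arm (12.1) |
|---|---|---|
| Any AE | Yes (9.2.1) | Yes |
| Device-related | Should be evaluated (9.2, 9.2.2) | Yes, as one yes/no class |
| Intensity | Must be determined (9.2.1) | No |
| Serious | Should be evaluated (9.2) | No; reported case by case (9.3) |
| Unanticipated | Should be evaluated (9.2, 9.2.2) | No; unanticipated problems notified case by case (9.3) |

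The acuity and slit-lamp summaries are ocular. They could reflect a marked ocular event, but mostly not the nasal, facial and headache events of section 9.2.3.

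**2. Illustration of what the planned counts can and cannot show**

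Inputs:
- 40 per arm. This is assumed: section 12.1 says approximately 80 will be randomized, the visible text gives no allocation ratio, and 80/2 = 40.
- Any AE in 24/40 in each arm, and device-related AEs in 20/40 in each arm. Both are assumed.
- Participants whose worst AE is moderate or severe: 10 v 2, 8 v 2 or 6 v 2 (active v sham). All are assumed and fall within the counts above.

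Method: for proportions p1 and p2 with Wilson limits (l1, u1) and (l2, u2), the Newcombe interval for d = p1 - p2 runs from d - sqrt[(p1 - l1)² + (u2 - p2)²] to d + sqrt[(u1 - p1)² + (p2 - l2)²]. P-values are from Fisher's exact test, two-sided.

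- *Any AE, 24 v 24.* Each arm 0.60, Wilson 0.446 to 0.737. d = 0; half-width sqrt(0.154² + 0.137²) = 0.206. Result: 0 points (-21 to 21).
- *Moderate or severe, 10 v 2.* 0.25 (0.142 to 0.402) and 0.05 (0.014 to 0.165). d = 0.20. Lower: 0.20 - sqrt(0.108² + 0.115²) = 0.042. Upper: 0.20 + sqrt(0.152² + 0.036²) = 0.356. Result: 20 points (4 to 36), p=0.025.
- *8 v 2.* d = 0.20 - 0.05 = 15 points, p=0.087.
- *6 v 2.* 0.15 (0.071 to 0.291) and 0.05 as above. Lower: 0.10 - sqrt(0.079² + 0.115²) = -0.040. Upper: 0.10 + sqrt(0.141² + 0.036²) = 0.245. Result: 10 points (-4 to 25), p=0.26.

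In all three splits the planned AE rows read 24 v 24 and 20 v 20. An intensity row would show the split each time, but only the largest is reasonably clear of chance.

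**The case against.** The strongest case against has five parts.

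- *Incidence may itself differ.* The sham delivers no current and goes in less deeply (section 4.1.3), and some listed events plausibly depend on stimulation. The any-AE or device-related count could then separate the arms. This stands as a limit: masking needs intensity to shift among participants who would have had an event anyway. Strong events in additional participants would raise the counts, although nothing would mark them as strong.
- *Serious events are not lost.* Section 9.3 makes serious AEs and unanticipated problems known case by case. This stands, and narrows the gap to non-serious moderate or severe events. It is not an arm comparison.
- *Further analysis is allowed.* Section 12.1 permits it but does not commit to it, and a table chosen once results are known carries less weight.
- *The study is small and exploratory, with no safety hypothesis, and the grades stay on the form whatever the plan says.* True. This limits what an added row can prove, but it does not explain leaving out a description that the collected data already support.
- *Some text is unseen.* Section 12.1 opens with redacted material, and the AE procedure (SOP012) is not in the file. An intensity table there cannot be ruled out, but the safety paragraph reads as complete.

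A reader might go further and infer that mild events will swamp the any-AE proportion in both arms, or that the plan would hide serious harm. The documents support neither: they give no AE rate for either arm, device-related AEs and ocular changes are also compared by arm, and serious AEs have their own reporting route.

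**Conclusion.** The point holds in a limited form. On the visible text, intensity is compulsory to record and seriousness is expected to be evaluated, yet neither enters a planned summary by arm. The consequence is conditional: the two AE counts miss a difference in intensity when it arises among participants who would report an event in either arm, and it concerns mainly non-serious moderate or severe events outside the eye.

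The size cannot be taken from the documents. Under the assumed 40 per arm and assumed equal AE counts, the planned rows stay the same for moderate-or-severe differences from 10 points (6 v 2, inconclusive) to 20 points (10 v 2, interval excluding zero). The change is worth making because it is nearly free and affects what the trial can say about tolerability. It does not undermine the efficacy analysis or case-level safety reporting.

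**What to change.** Add to the safety paragraph of section 12.1, by application and per participant:

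- number and percentage by worst AE intensity (none, mild, moderate, severe), once for all AEs and once for device-related AEs;
- number and percentage with at least one serious AE;
- for moderate-or-severe AEs, the risk difference with a 95% confidence interval, labelled descriptive.

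Optional rows are participants with an unanticipated device-related AE, and participants with an AE leading to discontinuation. The latter would come from the discontinuation form in section 10, since the documents do not show that item on the AE form.

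The cost is a few table rows from assessments the protocol already calls for, with no new procedure and no change in sample size. The drawback is wide intervals at this size (32 points across, from 4 to 36, in the 10 v 2 example), so the rows should be read as description and not as a test of safety.

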4.5.8.1 BULBAR AND LIMBAL HYPEREMIA

The redness of the bulbar and limbal conjunctiva of both eyes will be assessed using the EFRON Grading scale (0 to 4, 0 = no redness).

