4.5.8.2 CORNEAL AND CONJUNCTIVAL STAINING

A sodium fluorescein strip, wetted with a few drops of saline, will be applied to the superior bulbar conjunctiva of both eyes. Staining will be graded using the CCLR scale (0 to 100, 0 = no staining) while viewing with cobalt blue light through a Wratten no. 12 barrier filter.

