4.5.8.3 PALPEBRAL CONJUNCTIVAL HYPEREMIA AND ROUGHNESS

The redness and roughness of the upper and lower eyelids (tarsal plate zone 2) will be assessed using the CCLR scale (0 to 100, 0 = no redness/roughness).

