9.1 ADVERSE EVENT RECORDING

All AEs spontaneously reported by the participant and/or in response to an open question from study personnel or revealed by observation, physical examination or other diagnostic procedures will be recorded on the appropriate pages of the CRF. Any clinically relevant deterioration in clinical finding is considered an AE and should be recorded. When possible, signs and symptoms indicating a common underlying pathology should be noted as one comprehensive event.

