12 STATISTICAL ANALYSIS AND DATA MANAGEMENT

12.1 STATISTICAL ANALYSIS

[REDACTED]

[REDACTED] Descriptive statistics will be provided on information regarding baseline variables (age, gender, refractive error distribution, etc.).

Approximately 80 participants will be enrolled and randomized. This is an exploratory study and no formal sample size calculation was performed. The results from this study may be used to determine the appropriate time points and power for future studies.

Analysis of variables will be conducted separately on each eye, and data will not be pooled. The study eye will be defined as the qualified eye with the greatest increase in tear production with stimulation by a cotton swab at the Screening Visit (V1). If both eyes qualify and have the same increase in tear production with stimulation by a cotton swab, then the right eye will be designated as the study eye. Table 4 lists the exploratory outcome variables and anticipated statistical procedures.

Table 4: Statistical procedures

Variable	Analysis	Statistical test
Contact Lens Dry Eye Questionnaire-8 (CLDEQ-8), Comfort (scored immediately after insertion, after 2 hours and immediately before lens removal), Comfortable wear time and Total wear time	Descriptive statistics	Mean, Standard Deviation, Min, Max, Count by visit
	Effect of application by visit (comparison of change from baseline between application groups)	t -test / Wilcoxon rank-sum test (as appropriate)
	Stratified analyses by visit (comparison of change from baseline between application groups stratified by CL freq strata and CL type)	t -test / Wilcoxon rank-sum test (as appropriate)
Pre-lens non-invasive tear breakup time (NITBUT) and Tear meniscus height (TMH)	Descriptive statistics	Mean, Standard Deviation, Min, Max, Count by visit
	Effect of application by visit (comparison of change from baseline between application groups)	t -test / Wilcoxon -rank-sum test (as appropriate)

All data will be tested for normality of distribution using Shapiro-Wilk tests. The appropriate test will be selected based on tests of normality.

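### The slit-lamp safety rule of 2 or more grades is applied to both 0-4 and 0-100 scales, the visible text does not define a grade on the 0-100 scales, and neither the slit-lamp nor the acuity rule states a direction

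*Combined protocol and SAP*

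**What the plan says.** Section 12.1 names three safety assessments: adverse events, visual acuity and slit-lamp biomicroscopy. For the last two it plans counts and percentages of eyes by application, for instance of "eyes with a clinically significant change in visual acuity at each follow-up exam", with a matching summary for slit lamp at each visit.

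Two sentences define the events. For acuity, a clinically significant change "is defined as a change of more than 2 lines (logMAR score change greater than 0.2". For slit lamp: "A clinically significant change in the slit lamp biomicroscopy parameters will be a change of 2 or more grades". Neither says whether the change must be for the worse.

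Section 4.5.8 lists what is assessed at the slit lamp, on two kinds of scale:

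- Bulbar and limbal hyperemia (4.5.8.1): "will be assessed using the EFRON Grading scale (0 to 4, 0 = no redness".
- Corneal and conjunctival staining (4.5.8.2): "Staining will be graded using the CCLR scale (0 to 100, 0 = no staining".
- Palpebral hyperemia and roughness (4.5.8.3): "will be assessed using the CCLR scale (0 to 100, 0 = no redness/roughness".

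Section 9.1, on recording adverse events, does give a direction: "Any clinically relevant deterioration in clinical finding is considered an AE and should be recorded".

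**The concern.** A single threshold in grades has a plain meaning on a 0-4 scale. On a 0-100 scale it has none until someone says what a grade is. Section 12.1 expresses the acuity threshold in both lines and logMAR, but the slit-lamp sentence that follows has no such translation. Two analysts could follow the plan in good faith and produce very different slit-lamp tables from the same scores. Within one table, the percentage of eyes with a clinically significant change would not mean the same thing from one parameter to the next.

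The missing direction is a separate matter. A safety table should show harm. If any change counts, eyes that improve are added to eyes that worsen. The device is meant to increase tear production. If ocular surface findings improved more in the active arm, an undirected count could make that arm look less safe. That is a possibility, not a prediction.

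If these choices are left until after unmasking, the cut-off and the direction could be picked with the results in view.

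**Working it through.** The plan gives no figure to reproduce here. The inputs are the threshold of 2 (12.1), the ranges 0-4 and 0-100 (4.5.8.1 to 4.5.8.3), the acuity threshold of more than 0.2 logMAR (12.1) and the entry acuity of 20/40 or better with contact lenses (4.2.3).

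**Threshold as a share of the range, one unit taken as one grade**

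- 0-4 scale: 2 / 4 = 0.50, or 50%.
- 0-100 scale: 2 / 100 = 0.02, or 2%.
- Ratio: 0.50 / 0.02 = 25.
- The 2-point cut-off re-expressed on 0-4, assuming linear scaling: 0.02 × 4 = 0.08 grade.

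The literal reading has some support, because 4.5.8.2 itself describes staining as graded on the 0-100 scale.

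**Other readings of the 0-100 cut-off**

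- Proportional to the 0-4 scale: 0.50 × 100 = 50 points.
- A grade as a band of points: the cut-off is 2 × band width. The documents give no width. Assumed widths of 10 or 20 points would give 20 or 40 points.

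So the cut-off could be 2, 50 or something between, and the visible text does not choose.

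**Scope for counting improvement**

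- 0-4 scale: only an eye at grade 2 or above at baseline can improve by 2 grades.
- 0-100 scale, literal: any eye at 2 points or above can improve by 2.
- 0-100 scale, proportional: only an eye at 50 points or above can improve by 50.
- Acuity: 2 lines × 0.1 logMAR per line (assumed) = 0.2, so the two units in the rule agree. The worst permitted entry level is log10(40/20) = 0.301 logMAR. Such an eye must end better than 0.301 − 0.2 = 0.101 logMAR to be counted as improved. Eyes that start better have less room.

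**Illustration only.** The documents give no standard deviations (SDs), so flag rates cannot be derived from them. Assume no true change and normally distributed differences on 0-100 with SD 2, 5 or 10 points, ignoring the floor at 0.

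- Literal 2-point rule, either direction, 2 × (1 − Φ(2/SD)): 32%, 69% and 84% of eyes.
- Literal 2-point rule, worsening only, 1 − Φ(2/SD): 16%, 34% and 42%.
- 50-point rule, either direction: practically no eyes.
- 2-grade rule on 0-4, either direction, assumed SD 0.3, 0.5 or 0.7 grade: under 0.5%.

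The verdict does not rest on these rates.

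**The case against.** The strongest answer is redaction. Text is blacked out at the start of 4.5 and of 12.1, and the exclusion list in 4.2.3 and section 4.4.2 are not shown. A definition of a grade on the 0-100 scales, or a threshold per parameter, could sit in any of these. This stands: on the scales, one can say only that the visible text has no definition. It is a weaker answer on direction, because both rule sentences appear in full with nothing blacked out inside them.

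A second answer is that the literal reading fits poorly with a rule meant to pick out clinically significant change. The authors may have had only the 0-4 grading scale in mind. That is plausible, but the rule as written covers the slit-lamp parameters without exception, so the cut-off for the others remains open. A reader might infer that it must be either 2 or 50 points. The documents do not support that, since an intermediate band width is equally compatible with them.

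A third answer is that the sentences concern safety, so worsening is understood, and that 9.1 captures clinically relevant deterioration anyway. A reader might infer the opposite, that the plan intends to count improvements as harm. It does not say so; it is silent. Section 9.1 governs the recording of adverse events and does not define these tables. It limits the damage but does not supply the missing word.

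Finally, the study calls itself exploratory and these tables are descriptive. That is correct, and it sets the severity.

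**Conclusion.** The point holds as a minor one. In the visible text, a stated safety threshold does not work on the 0-100 scales to which it is applied. Followed literally, it asks for 50% of the range on hyperemia of the bulbar and limbal conjunctiva and 2% on staining and the palpebral findings. Because other readings are open, the right description is that the 0-100 cut-off is undefined. The missing direction affects both slit lamp and acuity, two of the three named safety assessments. In practice it matters little for acuity and the 0-4 scale, and more on 0-100 if the rule is read literally.

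A reader might infer that the trial's safety conclusions are compromised. The documents do not support that. No test, sample size or stopping rule depends on these definitions, the raw scores can be re-tabulated, and deterioration is recorded separately as an adverse event.

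The conclusion assumes that no redacted text defines the 0-100 threshold. The share-of-range figures need only the printed scale limits. The 0.08-grade and 50-point equivalents also assume linear scaling.

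**What to change.** Before unmasking, reconcile the slit-lamp rule in 12.1 with 4.5.8.1 to 4.5.8.3.

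1. State the threshold separately for the 0-4 and the 0-100 scales. The investigators should choose and justify the 0-100 cut-off; none is proposed here. If redacted text already sets it, a cross-reference in 12.1 is enough.
2. State the direction for slit lamp and acuity: report worsening from baseline as the safety event, and tabulate any improvement separately.

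The cost is a few lines of wording in 12.1 and matching table layouts. It needs no new data, visits or participants.
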